#### Footnotes:

- 1. Research Blood Sample Collection: Research blood samples to be collected in ctDNA preservation tubes every 3 months (+/- 2 weeks) for up to 2 years from 3 month post-surgery. Please refer to the PHOENIX Investigator Laboratory Manual for further details.
- 2. Disease recurrence: A recurrence tumour tissue sample should be obtained for each patient who has tissue available from a biopsy or from surgery, performed routinely as part of standard patient care

IRAS Project Number: 249774

### **15.TRIAL TREATMENT**

Olaparib and durvalumab are the investigational medical products (IMPs) within PHOENIX (protocol version 9.0 onwards).

FOR DETAILS ON TRIAL TREATMENT INCLUDING DOSE SCHEDULE, DOSE MODIFICATIONS, PERMITTED AND CONTRAINDICATED CONCOMITANT MEDICATIONS AND TOXICITY MANAGEMENT PLEASE REFER TO SECTIONS 24 and 25.

Part 1 Olaparib monotherapy - Section 24

Part 2 – Olaparib and durvalumab combination therapy – Section 25

### **16.PHARMACOVIGILANCE**

### 16.1. Definitions

### Adverse Event (AE)

An AE is any untoward medical occurrence in a patient or clinical trial subject; the event does not necessarily have a causal relationship with the treatment or usage.

### **Serious Adverse Event (SAE)**

An SAE is any untoward medical occurrence that occurs after the patient has provided written informed consent for Trial Entry and within 30 days after surgery or 30 days (or 90 days for durvalumab) after the last administration of trial treatment for patients who commence trial treatment in PART 2 or patient withdrawal from the trial and:

- results in death,
- is life-threatening
- requires hospitalisation or prolongation of existing inpatients' hospitalisation
- results in persistent or significant disability or incapacity
- is a congenital anomaly or birth defect

Important AEs that are not immediately life-threatening or do not result in death or hospitalisation but may jeopardise the subject or may require intervention to prevent one of the other outcomes listed in the definition above, may also be considered serious.

According to National Cancer Institute Common Terminology Criteria for Adverse Events (NCI CTCAE) v5.0, Grade 4 events are life threatening events. Any Grade 4 event should therefore be considered an SAE.

Progression of the indicated disease, death due to progression of the indicated disease and planned hospital admissions (e.g. for surgery) are not considered SAEs and do not need to be reported as such but should be reported on the appropriate electronic case report form (eCRF) within the clinical database.

Pregnancy or aid in the conception of a child whilst participating in a trial is not itself considered an SAE but should be followed up for congenital anomalies or birth defects (see Section 16.9 for further information).

IRAS Project Number: 249774

### **Serious Adverse Reaction (SAR)**

A SAR is an SAE that is suspected as having a causal relationship to the IMP, as assessed by the investigator responsible for the care of the patient. A suspected causal relationship is defined as possibly, probably or definitely related (see definitions of causality table).

### **Definitions of causality**

Relationship	Description
Unrelated	There is no evidence of any causal relationship with the trial drug
Unlikely	There is little evidence to suggest there is a causal relationship (e.g. the event
	did not occur within a reasonable time after administration of the trial
	treatment). There is another reasonable explanation for the event (e.g. the
	patient's clinical condition, other concomitant treatment)
Possible	There is some evidence to suggest a causal relationship (e.g. because the event
	occurs within a reasonable time after administration of the trial treatment).
	However, the influence of other factors may have contributed to the event (e.g.
	the patient's clinical condition, other concomitant treatments)
Probable	There is evidence to suggest a causal relationship, and the influence of other
	factors is unlikely
Definitely	There is clear evidence to suggest a causal relationship, and other possible
	contributing factors can be ruled out
Not assessable	There is insufficient or incomplete evidence to make a clinical judgement of the
	causal relationship.

# **Suspected Unexpected Serious Adverse Reaction (SUSAR)**

A SUSAR is a SAR, the nature or severity of which is not consistent with the information set out in the Reference Safety Information (RSI).

### Reference Safety Information (RSI)

A list of medical events that defines which reactions are expected for the IMP within a given trial and thus determining which Serious Adverse Reactions (SARs) require expedited reporting. The RSI for PHOENIX is contained in a clearly identified section of the Investigator's Brochure (IB) for each IMP.

### Adverse Events of Special Interest (AESI) in patients receiving olaparib (Part 1 and Part 2)

In addition, selected AEs experienced by any patient who has commenced olaparib treatment meeting any of the criteria listed below are AESI, and are reportable to the ICR-CTSU in the same timeframe as SAEs as detailed in Section 16.3. Therefore for the purposes of pharmacovigilance reporting the below events should be considered serious:

- Any event of pneumonitis
- Any event of myelodysplastic syndromes (MDS)/acute myeloid leukaemia (AML)
- Any new primary malignancy

### Adverse Events of Special Interest (AESI) in patients who receive durvalumab (Part 2)

In addition, selected AEs experienced by any patient who has commenced treatment with durvalumab meeting any of the criteria listed below are AESI. **These AESI may be serious or non-serious.** If an AESI is

IRAS Project Number: 249774

defined as serious, sites should follow the SAE reporting procedure detailed in section 16.3. If an AESI is defined as non-serious, sites should report the event in the clinical trial database. If the Investigator has any questions in regards to an event being an Important Medical (adverse) Event, the Investigator should promptly contact the ICR-CTSU Trial Team. AESIs observed with durvalumab include:

- Diarrhoea / Colitis and intestinal perforation
- Pneumonitis / Interstitial lung disease (ILD)
- Hepatic events (please refer to section 16.8 for evaluation and reporting of Potential Hy's Law (PHL) cases)
- Intestinal perforations
- Endocrinopathies (i.e. events of hypophysitis/hypopituitarism, adrenal insufficiency, hyperthyroid events, hypothyroid events, thyroiditis, type I diabetes mellitus (which may present with diabetic ketoacidosis) and diabetes insipidus))
- Guillain-Barré syndrome
- Myasthenia gravis
- Rash / Dermatitis (including pemphigoid)
- Nephritis
- Pancreatic events
- Renal events
- Myocarditis
- Myositis / Polymyositis
- Neuropathy / neuromuscular toxicity (e.g. Guillain-Barré, and myasthenia gravis)
- Other inflammatory responses that are rare / less frequent with a potential immune-mediated
  aetiology include, but are not limited to, immune thrombocytopenia, subcutaneous injection site
  reaction, Immune-mediated neutropenia, immune-mediated cystitis, immune-mediated lung
  disease, sclerosing cholangitis pericarditis, sarcoidosis, uveitis, vasculitis, non-infectious meningitis
  and non-infectious encephalitis, other events involving the eye and skin, haematological and
  rheumatological events.

In addition, infusion-related reactions and hypersensitivity/anaphylactic reactions with a different underlying pharmacological aetiology are also considered AESIs.

Further information on these risks (e.g. presenting symptoms) can be found in the current version of the durvalumab IB. More specific guidelines for their evaluation and treatment are described in detail in the Dosing Modification and Toxicity Management Guidelines (please see Appendix 7). These guidelines have been prepared to assist the Investigator in the exercise of his/her clinical judgment in treating these types of toxicities. These guidelines apply to AEs considered causally related to the trial treatment/trial regimen by the reporting investigator.

# 16.2. Reporting AEs to ICR-CTSU

Any toxicity, sign or symptom that occurs after the patient has provided written informed consent for Trial Entry and within 30 days after surgery in PART 1 or up to 30 days (or 90 days for durvalumab) of the last administration of trial treatment for patients who commence trial treatment in PART 2, which is not unequivocally due to progression of disease, should be considered an AE.

IRAS Project Number: 249774

All AEs must be reported on the relevant eCRF and submitted to ICR-CTSU.

The severity of AEs should be graded according to the NCI CTCAE v5.0. For each AE, the highest grade

observed since the last visit should be reported.

Abnormal laboratory findings that meet the criteria for Grade 2 or above toxicity as defined by NCI CTCAE

v5.0 are considered to be clinically significant and should be reported as AEs.

Whenever one or more toxicity/sign/symptom corresponds to a disease or a well-defined syndrome only the

main disease/syndrome should be reported.

16.3. Reporting of SAEs to ICR-CTSU

Any SAE that occurs after the patient has provided written informed consent for Trial Entry and within 30

days after surgery in PART 1 or up to 30 days (or 90 days for durvalumab) following the last administration of trial treatment for patients who commence trial treatment in PART 2 or up to 30 days (or 90 days for

durvalumab) after patient has withdrawn from the trial must be reported.

Any SAEs that occur more than 30 days (or 90 days for durvalumab) after the last dose of trial treatment that,

in the opinion of the Principal Investigator, are related to the trial treatment should be reported to ICR-CTSU

if the Principal Investigator becomes aware of them.

Any case of MDS/AML or a new primary malignancy occurring after the 30 day (or 90 days for durvalumab)

follow up period should be reported to ICR-CTSU, whether or not it is considered an SAE, and regardless of

the investigator's assessment of causality.

All SAEs should be reported to ICR-CTSU within 24 hours of the Principal Investigator (or delegated Co-

investigator) becoming aware of the event, by completing the PHOENIX SAE form and emailing to:

[contact]

For the attention of the PHOENIX Trial Team

As much information as possible, including the Investigator's assessment of causality, must be reported to

ICR-CTSU in the first instance. Additional follow up information including final diagnosis and outcome should

be reported as soon as it is available.

All SAE forms must be completed, signed and dated by the Principal Investigator or delegated Co-investigator.

All reported SAEs and follow up information will be forwarded to AstraZeneca (AZ) upon receipt at ICR-CTSU.

16.4. Review of SAEs

The Chief Investigator (or designated representative) will assess all reported SAEs for causality. SAEs assessed

as having a causal relationship to trial treatment will be evaluated for expectedness based on the RSI

IRAS Project Number: 249774

contained in the relevant Investigator Brochure. (NB. The Chief Investigator cannot downgrade the Principal

Investigator's assessment of causality.)

SAEs assessed as having a causal relationship to trial treatment and as being unexpected (SUSARs) will undergo expedited reporting to the relevant authorities and all other interested parties by ICR-CTSU (see

Section 16.5).

 $Sites should \ respond \ as \ soon \ as \ possible \ to \ requests \ from \ the \ Chief \ Investigator \ or \ designated \ representative$ 

(via ICR-CTSU) for further information that may be required for final assessment of an SAE as soon as possible.

16.5. Expedited Reporting of SUSARs

If an SAE is identified as being a SUSAR by the Chief Investigator, and is fatal or life threatening, it will be

reported by ICR-CTSU to the MHRA, the Research Ethics Committee (REC), AZ and all other interested parties within 7 days of being notified of the event.

within 7 days of being notified of the event

If an SAE is identified as a SUSAR by the Chief Investigator, and is not fatal or life threatening, it will be

reported by ICR-CTSU to the MHRA, REC and AZ within 15 days of ICR-CTSU being notified of the event.

ICR-CTSU will report any additional relevant information to the MHRA, REC and AZ as soon as possible, or

within 8 days of the initial report of a fatal/life threatening SUSAR.

The Principal Investigators at all actively recruiting sites will be informed of any SUSARs occurring within the

trial at appropriate intervals.

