#### Olaparib dosing schedule:

• 300mg olaparib (2 x 150mg tablets) to be administered orally twice daily on a continuous schedule Day 1-28 of each 28 day cycle.

For Part 2 trial treatment a cycle consists of 28 days and the planned trial treatment duration is 12 months (13 cycles). Patients will continue on trial treatment for up to a maximum of 12 months with serial ctDNA blood samples collected every 4 weeks. Subsequently patients will be followed up every 3 months with serial ctDNA blood sample collection for up to 24 months from the Part 2 pre-treatment assessment visit (anticipated to be approximately 3 months post-surgery).

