### **Cohorts E-G**

All patients in cohorts F and G will be given the opportunity to receive trial treatment in PART 2 provided they are confirmed suitable to commence trial treatment. Patients in cohort E will not be eligible for trial treatment in PART 2. Therefore, a maximum of 23 patients may receive trial treatment within PART 2.

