# SECTION 25 PART 2: OLAPARIB AND DURVALUMAB COMBINATION THERAPY TRIAL TREATMENT INFORMATION COHORTS F & G

# 25. PART 2 OLAPARIB AND DURVALUMAB COMBINATION THERAPY: TRIAL TREATMENT INFORMATION COHORTS F & G

#### 25.1. Part 2 Trial Treatment

Olaparib and durvalumab are the IMP for Cohorts F & G in Part 2 of the trial. Eligible patients will receive olaparib and durvalumab combination therapy. Patients who are not eligible for durvalumab treatment can receive olaparib monotherapy.

For patients that are receiving pembrolizumab as SOC the washout period from last dose of pembrolizumab and start of durvalumab is 30 days. Further details can be found in Section 12.3.

Trial treatment details for olaparib and durvalumab are shown separately below. The Investigator should use clinical judgement when attributing a toxicity to olaparib or durvalumab when given in combination. The choice of toxicity management guidelines should be based on the investigator's assessment of the causal role of the individual IMPs. In situations where the assessment qualifies both IMP toxicity management guidelines for a particular toxicity, the more conservative dose modification and/or dose interruption should be applied.

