#### 25.1.1. Part 2 Duration of Trial Treatment

Patients will remain on trial treatment for 12 months (13 cycles) in PART 2.

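### The explicit duty to tell Principal Investigators of SUSARs is tied to actively recruiting sites, so read literally it lapses at closed sites still giving Part 2 treatment

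*Protocol*

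**What the plan says.** Three statements in the protocol govern who hears of a SUSAR.

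- **Section 16.4, all SUSARs:** they "will undergo expedited reporting to the relevant authorities and all other interested parties by ICR-CTSU".
- **Section 16.5, fatal or life-threatening SUSARs (7 days):** they are "reported by ICR-CTSU to the MHRA, the Research Ethics Committee (REC), AZ and all other interested parties".
- **Section 16.5, other SUSARs (15 days):** they are "reported by ICR-CTSU to the MHRA, REC and AZ within 15 days of ICR-CTSU being notified of the event". Interested parties are not mentioned here.

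Investigators are then dealt with in a separate sentence of 16.5: "The Principal Investigators at all actively recruiting sites will be informed of any SUSARs occurring within the" trial, at appropriate intervals. Sections 16.4 and 16.5 contain no sentence covering sites that have stopped recruiting but still treat or follow patients.

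On exposure, Section 25.1 says "Eligible patients will receive olaparib and durvalumab combination therapy", and olaparib alone is given to those who cannot have durvalumab. Section 25.1.1 says "Patients will remain on trial treatment for 12 months (13 cycles) in PART 2". The Trial Summary places the start at the "Part 2 pre-treatment assessment visit (anticipated to be approximately 3 months post-surgery"). Section 5.1 gives the ceiling for cohorts F and G: "Therefore, a maximum of 23 patients may receive trial treatment within PART 2".

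**The concern.** The trigger for telling investigators is recruitment, but the reason for telling them is that they have patients on the drugs. In this trial the two come apart for a long time. Part 2 is the longest exposure to trial drug in cohorts E-G, and it necessarily continues after the last patient has been entered.

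The rule is also lopsided. Under Section 16.3 a site closed to recruitment must still report its own SAEs within 24 hours, up to 30 days (90 days for durvalumab) after the last dose. Under Section 16.5 the same site is not named among those to be told of a SUSAR elsewhere in the trial.

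The information matters to these investigators. Section 1.2 says that durvalumab combinations with olaparib need further investigation. Section 25.1 asks the treating investigator to judge which of the two drugs caused a toxicity. A SUSAR at another site bears on that judgement and on what remaining patients should be told.

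No endpoint, sample size or decision rule is affected.

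**Working it through.** The plan gives no figure for this point, so there is none to reproduce. The check compares the text and then works out how long treatment outlasts recruitment.

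**1. Text.** Section 16.4 sends every SUSAR to interested parties. Section 16.5 repeats this for fatal or life-threatening SUSARs but names only the MHRA, REC and AZ for the rest, so the two sections disagree on that class. The term is not defined in either. Because 16.5 gives Principal Investigators their own sentence, with their own condition, the natural reading is that the earlier phrase was not meant to cover them.

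**2. Inputs for the timing.**
- Window: 14 days, about 0.5 month (Section 3.1).
- Surgery to Part 2: about 3 months (Trial Summary).
- Part 2 treatment: 12 months, 13 cycles of 28 days = 364 days (Section 25.1.1).
- Safety period after the last dose: 30 days, or 90 days (about 3 months) for durvalumab (Sections 16.2 and 16.3).
- Recruitment of cohorts E-G: about 24 months (Trial Summary).
- Part 2 patients: at most 23 (Section 5.1).

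**3. Time from the last patient's window start.**
- To last dose: 0.5 + 3 + 12 = 15.5 months. In days, with surgery the day after the window: 14 + 1 + 91 + 364 = 470.
- To the end of the durvalumab safety period: 15.5 + 3 = 18.5 months. In days: 470 + 90 = 560.

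**4. Patients affected.** Assume uniform entry over 24 months, with all 23 starting and completing Part 2. Treatment then runs from month 3.5 to month 15.5 after each patient's window start.
- Any Part 2 treatment after closure: 15.5/24 = 0.646; 0.646 × 23 = 14.9, about 15 patients.
- Whole course after closure: 3.5/24 × 23 = 3.4, about 3 patients.
- Still on treatment or in the safety period at some time after closure, if all receive durvalumab: 18.5/24 × 23 = 17.7, about 18 patients.

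**5. Share of treatment time after closure.** A patient entered in the last 3.5 months has all 12 months after closure. For those entered in the 12 months before that, the amount falls linearly from 12 to 0. The mean per patient is (3.5 × 12 + 12²/2)/24 = (42 + 72)/24 = 4.75 months, and 4.75/12 = 40%. Including the 90-day period gives (3.5 × 15 + 15²/2)/24 = (52.5 + 112.5)/24 = 6.9 of 15 months, about 46%.

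**The case against.** The strongest reply is that the sentence in 16.5 does not say that only recruiting sites are told. Section 16.4 sends every SUSAR to all other interested parties, and an investigator treating patients with the drug fits the ordinary meaning of that phrase. Other safety channels do not depend on recruitment. The IDSMC reviews emerging safety data and can be convened ad hoc (Section 17.5). It can release data through the TSC to the TMG and, if appropriate, to participants (Section 18.3). Investigators are also directed to the current durvalumab brochure. Reports to the MHRA, REC and AZ are unaffected.

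Much of this stands. A reader might infer that once recruitment closes no treating investigator would hear of a SUSAR. The documents do not support that: they show that no explicit duty remains, not that nobody would be told. But none of these channels guarantees notice to each Principal Investigator. IDSMC summaries go to the TMG and TSC, and investigators join the TMG only as appropriate (Section 18.1).

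The objection also limits the size. A reader might infer that most Part 2 exposure falls after closure. It does not: 15 of 23 counts patients with any treatment time after closure, and the share of treatment time is about 40%. Twenty-three is a ceiling. Patients may decline, be ineligible, stay on pembrolizumab or receive capecitabine (Sections 12 and 12.1), and cohort G may stop after 8 (Section 17.1.1). That section also warns that cohort F may recruit for longer than E and G, in which case many cohort G patients would be treated while recruitment is still open. The count of 18 applies 90 days to everyone, whereas olaparib-only patients have 30.

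**Conclusion.** The point holds as a wrongly scoped reporting rule. The only explicit duty to inform Principal Investigators of SUSARs is tied to recruitment, while trial treatment continues to about 15.5 months, and the durvalumab safety period to about 18.5 months, after the last patient starts the window. Read literally, the duty lapses at any closed site still dosing patients, and sooner at a site that closes early. The reference to interested parties does not reliably fill the gap, because it is undefined and 16.4 and 16.5 apply it differently.

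Under uniform accrual over 24 months with all 23 patients starting and completing, about 15 of 23 have some Part 2 treatment after closure, about 40% of total Part 2 treatment time. The counts are illustrative upper values for uptake: refusal, ineligibility and early stopping lower them, and an uneven accrual pattern could move them either way. The defect does not depend on them, since one Part 2 patient at a closed site is enough to expose it. It is a patient-safety wording point that should be corrected, with no bearing on any statistical result.

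**What to change.** In Section 16.5, replace the reference to actively recruiting sites with: *all sites open to recruitment and all sites with a patient on trial treatment or within the 30-day (90-day for durvalumab) safety follow-up*. Limiting this to safety follow-up, rather than all follow-up, avoids taking in sites whose remaining patients are only in long-term follow-up off trial drug.

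In Sections 16.4 and 16.5, define other interested parties and use the term in the same way for both classes of SUSAR.

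The cost is a short edit to the reporting text and a few additional notifications after recruitment closes. No dose, schedule or clinical rule changes.

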16.6. Follow up of Serious Adverse Events

SAEs should be followed up until clinical recovery is complete or until disease has stabilised. SAE outcomes

should be reported to ICR-CTSU using the relevant section of the SAE form as soon as the Principal

Investigator or designee becomes aware of the outcome.

16.7. Annual Reporting of Serious Adverse Reactions

An annual report will be provided to the MHRA and REC by ICR-CTSU at the end of the reporting year.

16.8. Liver Dysfunction (Hy's Law)

Hy's Law is based on the observation that pure hepatocellular injury sufficient to cause hyperbilirubinemia is an ominous indicator of the potential for a drug to cause serious liver injury. A diagnosis of potential drug-

induced liver injury caused by a trial treatment can only be determined/inferred by excluding other potential

causes of liver injury (e.g., other drugs or viral hepatitis) and by ruling out an obstructive cause for the

elevated bilirubin (e.g., alkaline phosphatase should not be substantially elevated).

